7.3 Reporting adverse events

All reportable AEs/SAEs/RUSAEs should be recorded from the point of surgery to the end of trial participation at 12 months (52 weeks) follow-up post-operatively.

SAEs must be reported directly onto REDCap **within 24 hours** of the blinded site Research Team becoming aware of the event. SAEs classed as possibly, probably or definitely related AND unexpected (RUSAEs) will be reported by ExeCTU to the Sponsor within 24 hours of ExeCTU staff becoming aware. The Sponsor is responsible for onward reporting of RUSAEs to the REC within 15 days of the event being reported to ExeCTU in REDCap. However, if the event results in death the SAE will be reported to the REC within 7 days of the event being reported to ExeCTU in REDCap.

The CI (in their role as site PI) or their delegate, is responsible for signing off reportable SAEs within the EDC system. This will be a role restricted task that only authorised users of the EDC can complete.

For each SAE the following information will be collected:

- full details in medical terms and case description
- event duration (start and end dates, if applicable)
- action taken
- outcome
- seriousness criteria
- causality (i.e. relatedness to intervention)

Any change of condition or other follow-up information should be updated directly onto REDCap as soon as it is available. Events will be followed up until the event has resolved or a final outcome has been reached. An outcome of 'unknown' is not considered to be an acceptable final outcome. An outcome of 'not yet resolved' is an acceptable final outcome for non-serious AEs at the end of a participant's involvement in a trial, and for SAEs at database lock.

Where SAE causality is initially assessed by an authorised delegate of the CI but not the CI themselves, the CI (in their role as CI, as opposed to site PI) will record a second assessment of causal relationship. The CI may upgrade the causality assessment (e.g. from not related to related) but may not downgrade the assessment (e.g. related to not related). Where a causal relationship is suggested, the CI will record an assessment of expectedness.

The TSC and DMC will periodically review SAE data to determine patterns and trends of events, or to identify safety issues, which would not be apparent on an individual case basis.

7.3.1 Safety reporting flowchart (figure 2)

7.4 Notification of deaths

All deaths occurring after randomisation until the 12-month post-operative time point, or participant withdrawal from the study, irrespective of their relationship to the trial treatment, should be reported to ExeCTU via REDCap as an SAE within 24 hours of identifying the death. In addition, if the CI becomes aware of a participant death outside this period, that appears to be related to the study intervention, this should also be reported as an RUSAE.

8 STATISTICS AND DATA ANALYSIS

8.1 Proposed sample size

The Research Team completed a pilot trial of elective THR patients, from the same population as the proposed trial population. The mean OARS score at 6 weeks post-operatively was 72.4 (N=126) in the source publication [28], compared with 72.9 in the pilot sample (N=17; 6 PSPA, 11 SPAIRE). The source publication included a combination of participants receiving hip and knee surgery; however, it is thought that OARS scores will be comparable in these groups. Whilst the mean scores were similar in the pilot sample and source publication, the standard deviation (SD) for the pilot data was higher at 24.9 compared with 17.5, which is likely due to the smaller sample size of the pilot trial. Therefore, the SD from the source publication was used to inform the sample size, with the upper bound of a one-sided 80% confidence interval (18.5) used in the calculation.

The OARS is a newly published early outcome score that currently has limited data available, and no other publications beyond the original score paper [28]. The OARS group have not yet published data regarding the Minimal Important Difference (MID, also reported as MCID – Minimal Clinical Important Difference), which is often used as the target difference for comparisons between groups.

Published data relating to the well-validated and widely used OHS by the same Oxford group, which is on a scale of 0-48, worst to best, was used to inform our figures for a reasonable MID for the OARS [33]. Although this is not ideal, this was the closest reasonable comparator available. The OHS has a corresponding MIC for an individual patient of 7.5 points and an MID of 5 points (for between-group comparisons) on the 0-48 scale [34]. Scaling up the OHS MID of 5 points to be in line with the 0-100 scale for the OARS, results in a scaled MID of 10 points, which we considered appropriate to use as a conservative target difference for sample size estimation based on OARS as the primary outcome.

To achieve 90% power to reject the null hypothesis of equal means when the population mean difference is 10 points with SD of 18.5 and with a two-sided significance level (alpha) of 0.025 (two comparisons: PSPA vs PA; SPAIRE vs PA), a total of 87 participants per treatment group is required. Allowing for a 15% drop out rate, this becomes 103 per group (309 in total).

Having had the opportunity to review means and SDs for the primary outcome across treatment groups at an interim period during trial conduct (including data from 187 participants), it was noted that the observed SDs were higher than the SD used to inform the original sample size calculation (18.5). Based on observed SDs across treatment groups, a revised sample size of 321 participants was determined. (To maintain blinding, the observed SDs used to inform the revised sample size are not presented here, but are recorded in an unblinded area of the Trial Master File.) It was also noted that completion rate of the primary outcome was approximately 95%, well in excess of the 85% completion rate assumed in the original sample size calculation. Hence, accounting for 5% loss to follow-up the revised recruitment target is 339 participants (an increase of 30 participants, or 10% of the original recruitment target). This increased sample size was recommended by the DMC in their meeting on 03 February 2025 and endorsed by the TSC in their meeting on 10 February 2025. NIHR then approved the amendment to increase the sample size accordingly.

8.2 Planned recruitment rate

The RDE completes approximately 800 THR procedures each year, and approximately 400 per year would be eligible for recruitment to this trial. Therefore, over the planned 2-year recruitment period, we will recruit the required sample size (339 participants) from a population of approximately 800 eligible patients. The trial will be supported by a Research Coordinator based at the Hip Unit of the RDE to assist the clinical team with recruitment activities. Eligible patients will be identified prior to pre-operative assessment and contacted via phone. Those interested in taking

part in the trial will be sent patient information leaflets. Patients will give informed consent to the trained research coordinator during their routine pre-operative assessment.

Two previous THR single-centre studies at the RDE of the same patient population using the same MAKO system have achieved a recruitment rate of approximately 71%, (i.e. 56 patients were approached to achieve the recruitment target of 40 participants). However, these were cohort studies, and as such did not require participants to attend additional research follow-up appointments, which was likely to increase the recruitment rate compared with studies involving additional follow-up. An ongoing RCT within the Knee Unit of the RDE, also using MAKO robotic-assistance, requires participants to attend five additional in-person follow-up appointments compared with standard care. This trial is currently achieving a recruitment rate of approximately 50%, i.e. 50% of eligible patients have agreed to take part in the trial. Therefore, in the proposed trial with a requirement for two additional remote patient follow-up periods, and the support of a research coordinator to assist with recruitment activities, we believe it is reasonable that we will achieve a recruitment rate of 50-70% for the proposed trial. Whilst this is higher than the recruitment rate of many NIHR-funded surgical RCTs, based on current studies being completed within the hip and knee units of the RDE, we believe this is an achievable recruitment rate.

Based on the eligible patient cohort of approximately 400 per year (800 over the 2-year recruitment period), the minimum recruitment rate to achieve full recruitment of 309 patients within 24 months is 39% (i.e. all 800 patients contacted in order to recruit 309). This provides an acceptable margin, such that full recruitment can still be achieved, even if the recruitment rate is below that anticipated, or if hospital capacity is reduced compared with previous years.

This recruitment target includes a 15% drop-out to ensure that the trial will still have the required power, and previous and current recruitment rates in both the RDE Hip and Knee Units have been used to estimate that the recruitment rate is achievable within the allocated time period. There are no competing studies for recruitment of the patient population.

Following revision of the recruitment target to 339 participants, it is anticipated that full recruitment will be achieved within the same timeframe as for the original recruitment target of 309 participants, due to the successful recruitment into the trial, exceeding the initial anticipated recruitment rate. It is noted that the anticipated non-completion of the primary outcome has been revised to 5%, reduced from the original 15%.

8.3 Participant flow through the trial

Participant flow through the trial, from initial screening to final 52-week follow-up, will be reported according to CONSORT guidelines [35].

8.4 Statistical analysis plan

A detailed statistical analysis plan will be developed during the recruitment phase of the trial, and will be approved by the Trial Steering Committee (TSC) prior to database lock. Following approval, any amendments to the SAP will be documented, with date and nature of amendment, and reason for amendment. Amendments to the SAP will be discussed with the TMG and TSC.

The primary analyses and selected sensitivity analyses will be performed by a statistician who is blinded to intervention allocation. These analyses will be performed following final data cleaning and database lock. Following unblinding of the trial team, after presentation of the primary analyses and consideration of the results of the trial, the remaining sensitivity analyses will be performed.

Participant characteristics at baseline will be presented descriptively within and across the three treatment groups. Continuous outcomes will be reported as the mean and standard deviation, plus

the median and either minimum/maximum or interquartile range. Categorical and binary variables will be reported as percentages. All outcomes will be reported descriptively using data for all followup times where reported. Demographic characteristics of participants who do not provide 6-week follow-up data (OARS) will also be presented, for comparison with characteristics of participants included in the primary analysis.

8.5 **Primary outcome analysis**

8.5.1 General principles

The primary outcome, OARS measured at 6-week follow-up, will be analysed using linear regression modelling with adjustment for minimisation factors (it is noted that OARS is not reported at baseline as it would not be appropriate to do so). For each of the two pairwise comparisons with PA, i.e. PSPA vs PA and SPAIRE vs PA, the between-group mean difference will be reported with a two-sided 95% confidence and p-value. To take into account the fact that there are two comparisons of interest, the threshold for significance for the primary outcome will be 0.025 (two-sided); this approach is consistent with the approach taken for the sample size calculation, although confidence intervals will be at the 95% level. In addition, a global p-value comparing means across all three treatment groups will be reported, plus the mean difference for SPAIRE vs PSPA and the associated two-sided 95% confidence interval.

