8.6 Analyses of secondary outcomes

8.6.1 General principles

For the secondary outcomes, the threshold for significance will be (two-sided) 0.025, and a global p-value comparing effects across all three treatment arms will be reported in addition to two-sided 95% CIs for all three pairwise comparisons; no corrections will be made for multiple testing, but p-values will be interpreted in the light of the number of comparisons being made.

Continuous PROM outcomes (OACS, SAPS, OHS, LEFS, EQ-5D-5L) will be analysed using the same principles as for OARS; OHS, LEFS and EQ-5D-5L will be collected at baseline, so baseline scores will be adjusted for. In addition, the four physical activity outcomes, the two sleep outcomes and the biomarkers, CK and CRP, will be analysed using these principles.

Time to discharge from hospital is to be measured in terms of the number of nights spent in hospital. It is anticipated that he majority of participants will be discharged on the day of surgery, so the number of nights spent in hospital will be 0. The number of nights spent in hospital will be reported descriptively by participant group, and also analysed using a negative binomial model, which will account for zero-inflation, with adjustment for minimisation variables.

Analgesia outcomes will be modelled using appropriate methods (i.e. linear regression modelling for dose outcomes and logistic regression modelling for binary outcomes).

Deaths will be reported descriptively, by allocated group, for the full period of the trial from randomisation to 12-month follow-up, and for the following time periods:

- Post-randomisation and pre-operative
- Peri-operative (within 24 hours of surgery)
- 1 day to 6 weeks post-operative
- More than 6 weeks to 52 weeks post-operative

Furthermore, the odds ratio for death (at any time during follow-up to 52 weeks post-operative) comparing PSPA vs PA, SPAIRE vs PA, and SPAIRE vs PSPA will be reported with two-sided 95% confidence intervals.

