12.2 Future adoption, implementation, and impact

If successful, it is anticipated that the results of this trial will provide the evidence necessary to plan a future multi-centre RCT to compare the best-performing tendon-sparing approach (PSPA or SPAIRE) identified in this efficacy trial with the gold standard PA, to assess whether the efficacy results are generalisable across the NHS. If only one of the experimental groups (PSPA or SPAIRE) is found to be superior to PA, that one will be taken forward as the intervention for the future trial. If both SPAIRE and PSPA are found to be superior to PA, then it is anticipated that the tendon-sparing approach that will be taken forward will be selected based on the following criteria, if known: which is easier to implement; which is more cost-effective to implement; participant feedback; and the mean differences and confidence intervals for PSPA vs PA and SPAIRE vs PA. If the selection of a single tendon-sparing approach is not possible, it may be justifiable to propose a 3-arm multi-centre effectiveness RCT. This multi-centre RCT would align with the aims of the NIHR Health Technology Assessment (HTA) programme, and would be in collaboration with NHS sites that have the same robotic-guidance system as currently used at the RDE. This is currently a limited number (12 sites) but is likely to be substantially higher by the time such a trial could commence, as robotic-assisted surgery is rolled out across the NHS.

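### The two primary contrasts are tested at two-sided 0.025 for multiplicity but reported with unadjusted 95% intervals, so interval and verdict can disagree

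*Protocol*

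**What the plan says.** Protocol section 8.5.1 analyses OARS at 6 weeks by linear regression adjusted for the minimisation factors. For each comparison with PA, "the between-group mean difference will be reported with a two-sided 95% confidence and p-value". The significance threshold is then set at two-sided 0.025, and the reason given is "To take into account the fact that there are two comparisons of interest". The text describes this as "consistent with the approach taken for the sample size calculation, although confidence intervals will be at the 95% level". It gives no reason for keeping the 95% level and does not say how to present a result on which test and interval differ.

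Section 8.1 sizes the trial with the same two-sided alpha of 0.025: "To achieve 90% power to reject the null hypothesis of equal means when the population mean difference is 10 points with SD of 18.5", giving 87 per group. Section 3.1 makes estimating the magnitude of any differences part of the primary objective, so the interval is a primary result in its own right.

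**The concern.** A two-sided test at 0.025 corresponds to a 97.5% interval. Pairing it with a 95% interval has two consequences.

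- The multiplicity adjustment reaches the p-values but not the intervals, although both describe the same two contrasts in the same analysis.
- When p lies between 0.025 and 0.05, the report will show an interval that excludes zero beside a statement that the difference is not significant. Many readers judge by the interval, and they would then draw a conclusion that the plan does not permit.

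What is at stake is how the primary result is reported and read. The type I error of the stated test is not in question.

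**Working it through.** **Inputs.** Alpha 0.025 two-sided per contrast, power 90%, difference 10, SD 18.5, 87 per group, 15% dropout (section 8.1); revised analysable total 321, or 107 per arm, with the revised SD withheld (section 8.1); 1:1:1 allocation (section 6.5); 95% intervals (section 8.5.1). Assumed: common SD, equal arms, normal estimates and no precision gain from covariates.

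**1. The plan's own figure.** The normal approximation gives n = 2 × (18.5/10)² × (2.241 + 1.282)² = 6.845 × 12.41 ≈ 85. The noncentral t calculation gives 87 (power 90.3%), as stated. Then 87/0.85 = 102.4, rounded up to 103, and 3 × 103 = 309. The sample size therefore reproduces at alpha 0.025.

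**2. Critical values.** A 95% interval uses z = 1.960. A two-sided 0.025 test uses z = 2.241. The ratio is 2.241/1.960 = 1.14. They disagree exactly when 1.960 < |z| ≤ 2.241, that is 0.025 < p ≤ 0.05.

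**3. Joint coverage.** Each contrast has variance 2σ²/n. The shared PA arm gives covariance σ²/n, so the correlation is 0.5. From the bivariate normal:

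| Interval level | P(both intervals cover) | Family-wise error if read as tests |
|---|---|---|
| 95% | 0.909 | 0.091 |
| 97.5% | 0.954 | 0.046 |

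These figures do not depend on the SD or the sample size.

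**4. The band in OARS points.** SE = 18.5 × √(2/87) = 2.805. The band runs from 1.960 × 2.805 = 5.50 to 2.241 × 2.805 = 6.29 points (5.52 to 6.32 with t quantiles on 258 degrees of freedom).

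**5. How often it happens.** With Z normal, mean δ/SE and unit variance, the chance per contrast is P(1.960 < |Z| ≤ 2.241). For at least one contrast, add the two chances and subtract the joint probability at correlation 0.5. At 87 per arm and SD 18.5:

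| True effects (points) | Per contrast | At least one contrast |
|---|---|---|
| 0 and 0 | 2.5% | 4.8% |
| 5 and 5 | 10.6% | 19.9% |
| 10 and 10 | 3.9% | 7.4% |

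For example, with both effects at 5: 0.1065 + 0.1065 − 0.0135 = 0.1995.

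**6. After the sample size revision.** If alpha 0.025, 90% power and a 10-point difference were kept, 107 per arm implies an SD of about 20.6. This is an assumption. It gives SE = 20.6 × √(2/107) = 2.82 and a band of about 5.5 to 6.3 points. The chances in step 5 become 4.8%, 19.9% and 7.5%. As a wider range at 107 per arm, SD 18.5 gives about 5.0 to 5.7 points, and the pilot SD of 24.9 (section 8.1) gives about 6.7 to 7.6.

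**The case against.** The strongest reply is that this is a disclosed choice. Section 8.5.1 gives one decision rule and states the interval level openly, so the formal verdict is never ambiguous. Family-wise error under that rule is about 4.6%. Disagreement also runs one way only: a result significant at 0.025 always has a 95% interval that excludes zero. At the 10-point target it affects under 4% of results per contrast. All of this stands, and it makes the point one of reporting. It does not explain why the adjustment that was thought necessary for the p-values is left off the primary estimates.

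Three stronger readings are tempting, and the protocol does not support them.

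- **That the mismatch distorts the choice of approach for the next trial.** Section 12.2 does list "the mean differences and confidence intervals for PSPA vs PA and SPAIRE vs PA" among its criteria, but only once both approaches have been found superior. By then both contrasts have passed 0.025 and both intervals exclude zero at either level, so the disagreement cannot arise.
- **That the secondary outcomes need the same change.** Section 8.6.1 uses the same pairing, but says that no multiplicity correction is made and that p-values will be read in the light of the number of comparisons. Those intervals are openly unadjusted.
- **That fixed 0.025 tests are a mistake because Holm has more power.** With both effects at 10 and 87 per arm, Holm raises the chance of showing both from 84.4% to 90.2%. However, the planned 90% per contrast is already met, no objective requires success on both, and the chance of at least one success stays at 97.1%. With effects of 10 and 0, the chance of a false claim for the ineffective approach rises from 2.5% to 4.5%, still within 5%. A 95% interval at Holm's second step would also weaken the joint coverage wanted here. Holm is a preference about efficiency; it corrects no error.

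**Conclusion.** The concern holds as a mismatch between test and interval for the two primary contrasts. The test controls family-wise error at about 4.6%. The reported intervals jointly cover about 91% of the time, where intervals matching the test would reach about 95.4%. Observed differences of about 5.5 to 6.3 points would give conflicting messages. The chance of at least one such result is about 5% with no effect, 20% with both effects at 5 points and 7% with both at 10.

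The coverage figures rest on equal arms, a common SD and normal estimates. The band rests on the stated 87 per arm and SD 18.5. It is almost the same at 107 per arm if the undisclosed revised SD is about 20.6, and otherwise scales in proportion to the SD. A reader should not infer that the primary test is invalid or that the trial is underpowered by its own standard.

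**What to change.** In section 8.5.1, report 97.5% confidence intervals for PSPA vs PA and SPAIRE vs PA as the intervals that match the 0.025 test. If 95% intervals are also shown for these contrasts, label them as unadjusted for multiplicity. Leave the 0.025 threshold and the secondary-outcome reporting as they are.

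The cost is a wording change and primary intervals about 14% wider, for example a half-width of 6.3 points in place of 5.5. Sample size, data collection and the decision rule do not change. Leaving the decision rule alone also matters because section 8.1 records that group means and SDs were reviewed during the trial. Section 8.4 has the SAP approved before database lock, so the change can be made there and in the protocol by then.

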8.5.2 Estimands framework

To fit with the estimands framework, a treatment policy approach will be used to deal with intercurrent events that relate to receipt of treatment, e.g. receipt of THR not as allocated, or failure to receive THR (for those outcomes that are valid in absence of THR). Deaths during the trial will be handled using the 'while alive' approach; participant data collected prior to death will be included in the analyses. In the event of death prior to 6-week follow-up, the outcome data will be deemed as 'non-existent' and will not be imputed.

As a sensitivity analysis, a principal stratum approach will be used, repeating the analysis including only those participants who received THR as allocated; these participants will be considered as 'always compliers' i.e. they will always receive treatment as allocated.

